1. STUDY OBJECTIVES AND ENDPOINTS

1.1. Primary Objective and Endpoint

Primary Objective

- To evaluate the efficacy of BIIB059 in reducing disease activity in SLE subjects with active skin manifestations and joint involvement (Part A), and in subjects with active CLE (subacute CLE [SCLE] or chronic CLE [CCLE], including discoid lupus erythematosus [DLE]) with or without systemic manifestations (Part B).

Primary Endpoints

- Part A: Change in active joint count (28-joint assessment) from baseline to Week 24. The active joint count is defined as the sum of the tender joint count and the swollen joint count.
- Part B: Percent change in Cutaneous Lupus Erythematosus Disease Area and Severity Index-Activity (CLASI-A) score from baseline to Week 16.

1.2. Secondary Objectives and Endpoints

Secondary Objective

- To evaluate additional efficacy parameters of BIIB059 in reducing SLE/CLE disease activity
- To evaluate the safety and tolerability of BIIB059
- To evaluate the pharmacokinetic (PK) of BIIB059

Secondary Endpoints

Efficacy endpoints:

- Proportion of subjects with a CLASI-50 response, defined as a 50% improvement from baseline in CLASI-A score, at Week 24 (Part A) and at Weeks 12 and 16 (Part B).
- Percent change in CLASI-A score from Baseline to Week 12, Week 16, and Week 24 (Part A) and Week 12 (Part B).

CONFIDENTIAL

The information contained herein may not be used, disclosed, or published without the written consent of Biogen MA Inc.

- Proportion of subjects with a ≥ 4 -point reduction in CLASI-A score at Week 24 (Part A) and at Weeks 12 and 16 (Part B) compared with baseline.
- Proportion of subjects with a ≥ 7 -point reduction in CLASI-A score at Week 24 (Part A) and at Weeks 12 and 16 (Part B) compared with baseline.
- Proportion of subjects achieving a SLE Responder Index (SRI) of ≥ 4 (SRI-4) at Week 24 (see [Section 6.3.5](#) for a detailed description of this endpoint) (Part A only).
- Change from baseline to Week 24 in Systemic lupus erythematosus disease activity index 2000 (SLEDAI-2K) score (Part A only).
- Proportion of subjects with no new organ system affected, as defined by no new BILAG-2004 grade A and no more than one new BILAG-2004 grade B, from baseline at Week 24 (Part A only).
- Change from baseline to Week 24 in PGA of SLE (VAS) score (Part A only).

Pharmacokinetics Endpoints (Part A and Part B):

- PK parameters, including, but not limited to, clearance (Cl), volume of distribution (Vd) and absorption rate (ka).

Safety and Tolerability Endpoints (Part A and Part B):

- Incidence, nature, severity, and relationship to study treatment of adverse events (AEs) and serious adverse events (SAEs)
- Change/shift from baseline in standard laboratory parameters, vital signs and electrocardiogram (ECG) results
- Incidence of anti-BIIB059 antibodies in serum
- Absolute and percent change from baseline over time in immunoglobulin levels (IgA, IgG and IgM) and immunoglobulin titers for tetanus, diphtheria, and Pneumococcus vaccines

[REDACTED]

[REDACTED]

- [REDACTED]
- [REDACTED]

CONFIDENTIAL

The information contained herein may not be used, disclosed, or published without the written consent of Biogen MA Inc.

CONFIDENTIAL

2. STUDY DESIGN

2.1. Study Overview

This is a 2-part randomized, double-blind, parallel-group, placebo-controlled, multicenter Phase 2 trial. The protocol version 1 (PV1) was designed to evaluate the efficacy and safety of BIIB059 in SLE subjects with active skin manifestations (Part A) or active CLE, defined as discoid or subacute subtypes, with or without SLE (Part B). The study was to be conducted at approximately 95 centers in the United States, Europe, Latin America and Asia. In PV1 Part A, 100 subjects were planned to be randomly assigned to 1 of 4 treatment groups in a 1:1:1:1 ratio and receive either fixed doses of BIIB059 (50, 150 or 450 mg) or placebo subcutaneously Q4W for 24 weeks with a loading dose at Week 2, for a total of 7 doses. Randomization was stratified by baseline CLASI-A score (≤ 10 , >10) and prior oral corticosteroid usage (≤ 10 mg/d, >10 mg/d). In PV1 Part B, 30 subjects were planned to be randomly assigned to 1 of 2 treatment groups in a 2:1 ratio (20 subjects to BIIB059, 10 subjects to placebo) and receive either a fixed dose of BIIB059 (450 mg) or placebo SC Q4W for 12 weeks with a loading dose at Week 2, for a total of 4 doses. Randomization was stratified by CLASI-A score (≤ 10 , >10) and SLE (presence, absence).

2.1.1. Protocol changes

The protocol was first amended on 16 May 2017. Protocol version 2 (PV2) was designed to evaluate the efficacy and safety of BIIB059 in subjects with SLE and active skin manifestations and joint involvement (Part A) or active CLE, defined as SCLE or CCLE, including DLE, with or without SLE (Part B). As part of the amendment, the number of sites was expanded to approximately 130 centers across United States, Europe, Latin America, and Asia. Two additional amendments were done after PV2 but were administrative in nature and didn't impact the study design and statistical analyses plan.

The key changes between PV1 and PV2 (and subsequent versions) are listed below:

Part A

- In PV2 (and subsequent versions), oral corticosteroid tapering in Part A is now mandatory. Under PV1, it was encouraged but was not mandatory.

CONFIDENTIAL

The information contained herein may not be used, disclosed, or published without the written consent of Biogen MA Inc.

- In PV2 (and subsequent versions), the subjects will be randomized to fixed dose of BIIB059 450 mg or placebo. In PV1, subjects were planned to be randomized to either fixed doses of BIIB059 (50, 150 or 450 mg) or placebo.
- In PV2 (and subsequent versions), change in inclusion criteria included: removal of the CLASI-A score requirement of 8 or higher at entry and addition of joint count, requiring at least 4 swollen and 4 tender joints based on assessment of 28 joints (see Section 4.3.3 of the protocol), with at least 4 occurring in the PIP, MCP, or wrist joints. Note: A joint that is both tender and swollen will be included in both categories (counts as 1 tender and 1 swollen).

[figure not shown]
Part B

- In PV1, last dose was originally planned at week 8, with end of treatment period at week 12. Under PV2 (and subsequent versions), an additional week 12 dose was added (with end of treatment period now moved to week 16).
- In PV2 (and subsequent versions), the subjects will be randomized to either fixed doses of BIIB059 (50, 150 or 450 mg) or placebo. In PV1, subjects were to be randomized to fixed dose of BIIB059 450 mg or placebo.

The study design for PV2 (and subsequent versions) Part A and Part B is shown in Figure 1 and Figure 2 below:

CONFIDENTIAL

[figure not shown]
The information contained herein may not be used, disclosed, or published without the written consent of Biogen MA Inc.

Figure 1: Study Design PV2 (and subsequent versions) Part A

Abbreviations: ANA=antinuclear antigen; dsDNA= double-stranded DNA; FU=follow-up visit; MCP=metacarpophalangeal joints; OCS=oral corticosteroid; PIP=proximal interphalangeal joints; Q4W=every 4 weeks; SoC=standard of care; TD1=Treatment Day 1. ** At least 4 of the swollen joints must be PIP, MCP, and/or wrist joints. A joint that is both tender and swollen will be included in both categories (counts as 1 tender and 1 swollen). Black triangles represent dosing visits.

CONFIDENTIAL

The information contained herein may not be used, disclosed, or published without the written consent of Biogen MA Inc.

Figure 2 Study Design PV2 (and subsequent versions) Part B

Abbreviations: CLASI-A=Cutaneous Lupus Erythematosus Disease Area and Severity Index- Activity Scale; CLE=cutaneous lupus erythematosus; FU=follow-up visit; OCS=oral corticosteroid; Q4W=every 4 weeks; SoC=standard of care; TD1=Treatment Day 1

1 Histologically confirmed in the past or at Screening.

Black triangles represent dosing visits

CONFIDENTIAL

The information contained herein may not be used, disclosed, or published without the written consent of Biogen MA Inc.

2.1.2. Subject recruitment and treatment

In Part A (PV2), approximately 100 subjects will be randomized to receive either subcutaneous injections of 450 mg BIIB059 or placebo in a 1:1 ratio every 4 weeks (Q4W) for 24 weeks, with an additional dose at Week 2 (for a total of 7 doses, Figure 1). Up to 70 additional subjects may be added at the interim analysis (see [Section 10](#)). Randomization will be stratified by oral corticosteroid usage (≤ 10 mg vs. > 10 mg) and by geographic region (United States vs. Asia vs. Latin America and Europe). In Part A (PV1), prior to the amendment, subjects were randomly assigned to 1 of 4 treatment groups in a 1:1:1:1 ratio and received either fixed doses of BIIB059 (50, 150 or 450 mg) or placebo. Randomization, in Part A (PV1), was stratified by oral corticosteroid usage (≤ 10 mg vs. > 10 mg) and by CLASI-A score (≤ 10 vs. > 10). Subjects who have been enrolled in PV1 before the amendment were to remain on their original treatment assignment and were not allowed to reconsent under PV2 and subsequent version.

In Part B (PV2), approximately 100 subjects will be randomized to 1 of 4 treatment groups in a 1:1:1:1 ratio and will receive either fixed doses of BIIB059 (50, 150 or 450 mg) or placebo subcutaneously every 4 weeks (Q4W) for 16 weeks, with an additional dose at week 2, for a total of 5 doses (Figure 2). Randomization will be stratified by CLASI-A score (≤ 10 vs. > 10) and DLE (presence, absence). In Part B (PV1), prior to the amendment, subjects were randomized to either 450 mg BIIB059 or placebo (in a 2:1 ratio). Randomization, in Part B (PV1), was stratified by SLE status (presence, absence) and by CLASI-A score (≤ 10 vs. > 10). Subjects enrolled under PV1 were to remain on their original treatment assignment but could be reconsented under PV2 and subsequent versions.

Additional details of the study design can be found in full protocol of 230LE201.

CONFIDENTIAL

The information contained herein may not be used, disclosed, or published without the written consent of Biogen MA Inc.

 Biogen	Statistical Analysis Plan 230LE201	<V 2.0>
--	---	----------------------

This statistical analysis plan covers the planned analyses for both the unblinded IA and the final analyses (Part A and Part B). All efficacy, safety and PK endpoints described in this plan will be included in the final analyses, while a subset of the endpoints will be included in the unblinded IA (see [Appendix B](#) for more details). For each endpoint, the same analysis method will be used for both the interim and final analyses, unless otherwise specified.

Within each part (Part A and Part B), all data will be summarized by treatment group. In addition for each part (Part A and Part B), the data described in [Section 5](#) which includes patient disposition, baseline characteristics and demography data, and concomitant medications will be summarized overall, and the safety data described in [Section 7](#) will also be summarized for all BIIB059 groups combined.

A pooled analysis (pooled data from Part A and Part B) may also be performed on Part B endpoints associated with CLASI-A assessment. Only the data from Part A subjects that meet the following criteria will be pooled (by treatment group) for the combined (Part A and Part B) analyses:

- Baseline CLASI-A ≥ 8

The pooled analyses will be performed using the same analysis method as for the CLASI-A endpoints within Part B, where applicable.

The statistical software, SAS® version 9.3 or above, will be used for all summaries and analyses.

CONFIDENTIAL

The information contained herein may not be used, disclosed, or published without the written consent of Biogen MA Inc.

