³ Between Weeks 5 and 7 (Rescue 2) and between Weeks 9 and 11 (Rescue 3), the dose can be increased to the previous dose level for up to 1 week before restarting the tapering schedule.

11.4.1.1.2.3. Part B Specific Instructions

Oral Corticosteroid

No corticosteroid tapering schedule is planned for subjects in Part B. The dose of corticosteroids given at Screening should not exceed 15 mg/day and should remain stable (no increase throughout the Screening, Treatment, and Follow-up Periods).

An increase of corticosteroid dose will be considered a treatment failure (see Section [16.1.2.1](#)). Subjects are allowed to remain in study and receive the investigational product.

11.4.1.1.2.4. Subject Diaries

Subjects will be issued a paper diary to record daily corticosteroid use (topical and oral) between study visits. Subjects will be instructed to bring the diary to the clinic at each visit, where it will be collected and reviewed by site personnel.

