Rescue 1	Week 1-4 ² (Day 1 to 28)	Stable 1 OCS rescue for SLE activity allowed up to maximum 10mg/day above Day 1 dosage, but must return to Day 1 level within 7 days							
Rescue 2	Week 5³ (Day 29 to 35)	17.5	15	12.5	10	7.5	7.5	5 or 2.5	2.5 \leftarrow to <5
	Week 6³ (Day 36 to 43)	17.5	15	12.5	10	7.5	7.5	5 or 2.5	2.5 \leftarrow to <5
	Week 7³ (Day 44 to 50)	15	12.5	10 12.5	^{10 or} 7.5	7.5	7.5 or 5	5 or 2.5	2.5 \leftarrow to <5
	Week 8 (Days 51 to 57)	12.5 15	12.5	10	^{10 or} 7.5	7.5	7.5 or 5	5 or 2.5	0 or 2.5 \leftarrow to <5
Rescue 3	Week 9³ (Days 58 to 64)	12.5	10	10 or 7.5	7.5	7.5 or 5	7.25 or 5*	5 or 2.5	0 or to 2.5 \leftarrow to <5
	Week 10³ (Days 65 to 71)	12.5	10	10	7.5	5	2.5	2.5	0 to 2.5

CONFIDENTIAL

The information contained herein may not be used, disclosed, or published without the written consent of Biogen MA Inc.

Allowable OCS Rescue Dosing ¹	Timing by Weeks (Days)	Corticosteroid OCS Starting Dose Prior to Tapering (mg/day)							
		20 mg	17.5 mg	15 mg	12.5 mg	10 mg	7.5 mg	5 mg	2.5 ← to <5 mg
	Week 11 ³ (Days 72 to 78)	10	10 or 7.5	7.5 or 5	7.5 or 5	7.5 or to <5	5 or 2.5	2.5	0 or to 2.5 ←
	Week 11-12 (Days 79 to 85)	Stable at Week 10 dose 10	7.5	7.5	5	2.5 to <5	2.5	2.5	0 to 2.5
	Week 13-16 (Days 86 to 113)	Stable or Decrease by 2.5 mg as tolerated. 1 OCS rescue for SLE activity allowed up to Day 1 corticosteroid at Week 12 dose (maximum 20 mg/day), however must be returned to week 12 level within 7 days or decrease							
	Week 17-24 (Days 114 to 169)	Stable at Week 16 dose							

Abbreviations: OCS = oral corticosteroids; SLE = systemic lupus erythematosus.

¹ Two rescues are allowed out of the three described.

² Between Week 1 and 4 (Rescue 1). Once a dose is reduced it can be maintained stable but must not be re-increased, with the exception of the 1 time rescue.

³ Between Week 5 and Week 7 (Rescue 2) and between Week 1 and 49 and 11(Rescue 3), the dose can be increased to the previous dose level for up to 1 week before restarting the tapering schedule.

² One oral corticosteroid rescue for SLE activity allowed up to a dose no higher than baseline level, but must be returned to last OCS dosage prior to rescue level within 7 days

Rationale: A lower therapeutic level of corticosteroid (or complete washout) will lower the responder rate in the placebo group.

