6.1.2. Part B Efficacy Analyses Considerations

Continuous endpoint

All Part B continuous efficacy endpoints will be analyzed using the following described method, unless otherwise specified.

A Mixed Effect Model Repeat Measurement (MMRM) model will be used as the primary method to analyze endpoint of interest using treatment group, study visit (week 2, 4, 8, 12, 16),

CONFIDENTIAL

The information contained herein may not be used, disclosed, or published without the written consent of Biogen MA Inc.

 Biogen	Statistical Analysis Plan 230LE201	<V 2.0>
--	---	----------------------

study visit-by-treatment interaction, DLE (Yes/No), CLASI-A score (≤ 10 vs. > 10), baseline value of the endpoint and baseline-by-visit interaction as fixed effect covariates. An unstructured covariance matrix will be used to model the within-patient variance-covariance errors. If the unstructured covariance structure matrix results in a lack of convergence, the heterogeneous Toeplitz covariance structure followed by the heterogeneous first-order autoregressive covariance structure will be used. The Kenward-Roger approximation will be used to estimate the denominator degrees of freedom. The primary treatment comparison between each BIIB059 treated group and placebo will be at the end of the Week 16. Handling of missing data and data from treatment failures subjects is provided in [Section 6.6](#).

Binary endpoint

The binary endpoints will be analyzed using logistic regression with covariates of treatment and DLE (Yes/No) and CLASI-A score (≤ 10 vs. > 10). For binary endpoints dichotomized from a continuous endpoint (such as PGA VAS < 1 point increase, the baseline of the continuous endpoint will be added to the above covariates list. The odds ratio, its 95% CI and the p-value for each BIIB059 dose compared to placebo will be presented. Early discontinuation(s) and/or treatment failures will be handled using non-responder imputation approach as discussed in [Section 6.6](#).

[REDACTED]

[REDACTED]

[REDACTED]

[REDACTED]

[REDACTED]

[REDACTED]

Censoring rules: Subjects who do not experience an event by Week 16 or early termination will be censored at the date of last assessment during the treatment period. The start date for calculation of day to censor or event will be the date of first dose.

CONFIDENTIAL

The information contained herein may not be used, disclosed, or published without the written consent of Biogen MA Inc.

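### If the optional combined Part A + Part B CLASI-A analysis is run as written, the 50 mg and 150 mg contrasts absorb part of any difference between the two parts, because the reused Part B model shows no term for study part

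*SAP*

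**What the plan says.** SAP 3.1 makes separate Part A and Part B analyses the rule, then adds an option: "A pooled analysis (pooled data from Part A and Part B) may also be performed on Part B endpoints associated with CLASI-A assessment". The merge is by treatment label, with one filter on Part A, a baseline CLASI-A of at least 8: "Only the data from Part A subjects that meet the following criteria will be pooled (by treatment group) for the combined" analyses. The method is the Part B one: "The pooled analyses will be performed using the same analysis method as for the CLASI-A endpoints within Part B, where applicable".

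That method is in SAP 6.1.2. The MMRM has treatment, visit, visit-by-treatment, and "DLE (Yes/No), CLASI-A score (≤ 10 vs. > 10), baseline value of the endpoint and baseline-by-visit interaction as fixed effect covariates". The binary endpoints use "logistic regression with covariates of treatment and DLE (Yes/No) and CLASI-A score". Neither list contains study part. The protocol's Part B MMRM (16.1.2.1) has SLE presence as a factor, which would be a partial proxy for part because every Part A subject has SLE. The SAP model does not carry it.

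Allocation differs between the parts. Part A randomises 1:1 to 450 mg or placebo from version 2 on (Protocol 16; SAP 2.1.2). Under version 1 it used four equal arms and enrolled up to about 20 subjects. Part B randomises 1:1:1:1 with 25 per arm, after a version 1 stage of 20 on 450 mg and 10 on placebo (SAP 2.1).

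Conduct differs too. The Part A oral corticosteroid taper is mandatory from version 2 (SAP 2.1.1). For Part B, Protocol 11.4.1.1.2.3 states: "No corticosteroid tapering schedule is planned for subjects in Part B".

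**The concern.** Randomisation protects dose-placebo comparisons within a part. Merging two parts with different allocation ratios gives up that protection unless the model conditions on part. Here pooled placebo would be 42% to 53% Part A under the counts assumed below, against 17% for each low-dose arm. The 50 mg and 150 mg contrasts would then include a share of any A-B difference in CLASI-A change, with no drug effect needed.

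A difference is plausible. Part A enrols SLE with active arthritis and Part B enrols histologically confirmed CLE, and the steroid rules differ. The CLASI-A filter aligns entry severity only.

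The 450 mg contrast is nearly balanced, so the distortion would shift the low doses relative to 450 mg. A reader of a pooled dose comparison would want exactly that ordering to be right.

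**Working it through.** **The plan's own figure.** The documents give no power or error rate for the combined analysis. The nearest figure is Part B's roughly 90% power for MCP-Mod (Protocol 16.8; SAP 11). With 20 completers per arm (25 less 20%), SD 30, maximal difference 27.5, one-sided 5%, the five SAP 6.2.1 shapes and critical value 1.98, power is 89% to 94% by shape. The figure reproduces, so SD 30 is used below.

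**Inputs (placebo/50/150/450 mg).**
- Part B with version 1 at its planned size: 25+10 / 25 / 25 / 25+20 = 35/25/25/45.
- Part A version 1: 20/4 = 5 per arm. Version 1 required CLASI-A of at least 8, so all pass the filter.
- Part A version 2 or later: the number passing the filter is not documented. Assumed 20 to 35 per arm, on placebo and 450 mg only. That is 40% to 70% of 50 per arm; 35 is also 41% of the 85 per arm reached if 70 subjects are added.
- Part A total: 25/5/5/25 to 40/5/5/40.
- The A-B difference D is not documented. Taken as 5, 10, 15 and 20 points, the same for all Part A subjects.

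**Bias.** Bias = D × (Part A share of placebo − Part A share of the dose arm).
- Lower case: 25/60 − 5/30 = 0.417 − 0.167 = 0.25.
- Upper case: 40/75 − 5/30 = 0.533 − 0.167 = 0.367.
- For 450 mg: 25/60 − 25/70 = 0.06, and 40/75 − 40/85 = 0.06.

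**Standard error.** SE = 30 × √(1/n_placebo + 1/n_dose).
- Lower case: 30 × √(1/60 + 1/30) = 6.71.
- Upper case: 30 × √(1/75 + 1/30) = 6.48.

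**Two-sided rejection with no drug effect.** 1 − Φ(1.96 − bias/SE) + Φ(−1.96 − bias/SE). At D = 15 in the upper case, bias = 5.5 and bias/SE = 0.849, giving 0.133 + 0.002 = 13.6%.

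| D (points) | Bias, 50 or 150 mg vs placebo | Two-sided error (nominal 5%) |
|---|---|---|
| 5 | 1.25 to 1.83 | 5.4% to 5.9% |
| 10 | 2.50 to 3.67 | 6.6% to 8.7% |
| 15 | 3.75 to 5.50 | 8.7% to 13.6% |
| 20 | 5.00 to 7.33 | 11.6% to 20.5% |

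With 20% dropout, the 15-point row becomes 7.9% to 11.8%. The 450 mg test stays between 5.0% and 5.8%.

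**MCP-Mod.** If 25%, 50% or 75% of Part A version 2 subjects pass the filter (20% dropout, no expansion) and Part A improves 20 points less, the one-sided 5% test rejects 8.5%, 11.6% and 14.8% of the time.

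**Effect of DLE adjustment.** A Week 16 ANCOVA was simulated with DLE, CLASI-A stratum and baseline, at the same three filter shares and D = 20. Error for 50 mg was 6.2%, 10.3% and 15.4% with equal DLE prevalence in the parts, and 5.4%, 8.4% and 11.1% with prevalences of 30% and 80%. The closed form at these shares gives 7.2%, 12.5% and 18.5%. It runs higher because it holds the SD at 30, while an unmodelled part difference also adds to residual variance.

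**Adding a plain A/B term.** If the difference is the same throughout Part A, simulated low-dose error returns to 4.4% to 5.6%. Least squares on the counts above gives a low-dose SE of 6.82 (6.71 × 1.016) to 6.67 (6.48 × 1.029), a rise of about 2% to 3%.

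**If the version 2 taper causes the difference.** All Part A low-dose subjects are version 1, while 20 of 25 to 35 of 40 Part A placebo subjects are version 2 or later. A 15-point taper gap gives bias of 15 × 20/60 = 5.0 to 15 × 35/75 = 7.0 with no term. Least squares with an A/B term leaves 2.6 to 3.0 points, a two-sided error of about 7%. Splitting Part A by version removes it. The low-dose SE becomes 6.98 (×1.041) to 6.86 (×1.059), a rise of about 4% to 6%.

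**The case against.** Four points weigh against this, and most of them stand.

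- **Optional and supplementary.** The combined analysis may be run or not. The primary dose-response test, model selection and target-dose estimation all sit in the Part B analysis (SAP 6.2.1), and SAP Appendix B lists no combined analysis in its visible text. A reader might infer that the trial's dose-response conclusion is compromised. It is not, because nothing here touches the Part B primary analysis.
- **Direction unknown.** A reader might infer that low doses will look falsely effective, citing the version 2 amendment summary's rationale for the taper: "A lower therapeutic level of corticosteroid (or complete washout) will lower the responder rate in the placebo group". That sentence justifies a stricter Part A taper against version 1. It speaks of responder rate, not CLASI-A percent change, and does not compare Part A with Part B. Part A subjects not on steroids are eligible (Protocol 11.4.1.1.2.2), so the taper does not affect everyone. The treatment-failure rules also differ (SAP 5.8): Part A permits Rescue 1, whereas in Part B any steroid increase above baseline, apart from permitted topicals, is a failure. That could push the other way.
- **Size assumed.** A residual gap of 15 to 20 points is 55% to 73% of the planned maximal effect of 27.5. At 5 points the inflation is trivial, and DLE adjustment may absorb some of a larger gap.
- **Redaction.** The method is reused only where applicable, and much of SAP 3.2, parts of 3.3, 6.8 and 6.9, and Appendices A1 and A2 are blacked out. An adjustment could be there. The documents support no visible term, not proof that none exists.

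What survives is the mechanism. Unequal allocation with no part term transmits any part difference to the low-dose contrasts, whichever way it runs.

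**Conclusion.** The concern holds in a limited form. Run as the visible text describes, the combined analysis would pass about 25% to 37% of any A-B difference in CLASI-A change into the 50 mg and 150 mg contrasts, and would affect the pooled MCP-Mod test. Error inflation ranges from negligible at 5 points to roughly two- to four-fold at 20 points. Those figures assume 25/5/5/25 to 40/5/5/40 qualifying Part A subjects, SD 30, full planned counts and a uniform part difference; none of the qualifying counts or the difference is documented.

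It would also be too strong to say that a plain Part A/Part B term restores nominal error in every case. It does so only if Part A is homogeneous across protocol versions, and the mandatory taper is a documented reason why it may not be.

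**What to change.** In SAP 3.1, state that any combined Part A + Part B CLASI-A model includes:

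- in the MMRM, a three-level factor (Part A version 1, Part A version 2 or later, Part B) and its interaction with visit;
- in the logistic models, the same factor;
- for MCP-Mod, contrasts applied to the means adjusted for this factor.

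A plain A/B term is the minimum, but it leaves residual bias if the version 2 taper drives the difference. If a redacted section already specifies an adjustment, a cross-reference from SAP 3.1 is enough.

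The cost is a sentence or two in the SAP and the precision loss derived above: about 4% to 6% on the low-dose standard errors with the three-level factor, or 2% to 3% with the A/B term. Fixing this before unblinding also avoids choosing the model after the results are known.
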